9.2.1. Other Adverse Events: Infusion Reactions

The incidence of infusion associated TEAEs by MedDRA SOC and PT will be summarized by treatment group and presented in a listing. This is a subset of the AEs where the question “Was the event an infusion-associated adverse event?” is checked “Yes”. Summaries will be repeated for all general baseline subgroups indicated in Section 6.

A separate summary will also be presented by planned infusion number. A TEAE will be counted based on AE and infusion start dates. For example, if an AE starts after infusion #2 but before infusion #3, the AE will be counted under infusion #2.

If applicable, the incidence of anaphylactic reaction, defined as the broad algorithmic SMQ of “Anaphylactic reaction” given in [Appendix 13](#) will be summarized by treatment group.

In order to explore the temporal relationship of TEAEs that may be associated with the infusion, the incidence of all TEAEs occurring within 24 hours (1 day) of an infusion will be summarized by treatment group and presented in a listing. In addition, for this subset of TEAEs, the following will be summarized by treatment group for any infusion and at each infusion overall and by PT:

- the number and percent of subjects infused
- the number and percent subjects experiencing an event within 24 hours
- the number of the events
- descriptive statistics for the number of events per subject
- descriptive statistics for the duration (days) of the events

TEAEs will be counted as occurring within 24 hours (1 day) of an infusion if:

- the start date/time of the TEAE is not missing and the infusion start date/time \leq the start date/time of the TEAE \leq the infusion start date/time + 24 hours or
- the start time of the TEAE is missing and the TEAE start date = the infusion start date or the TEAE start date = the infusion start date + 1 day.

9.3. Clinical Laboratory Evaluations

All laboratory assessments are given in [Appendix 10](#). Laboratory parameters will be summarized in standard international (SI) system of units.

The following normal ranges will be used where not provided in the central laboratory data:

- INR Upper Limit of Normal (ULN) = 1.1
- Creatinine Clearance Lower Limit of Normal (LLN) = 90 mL/sec = 1.5 mL/min
- eGFR LLN = 90 mL/min/1.73m²

All clinical laboratory data will be presented in by-subject data listings. In addition, separate listings will be presented for any subject with a post-baseline CTCAE grade 3 or 4 laboratory value. Normal ranges provided by the central laboratory will be presented in a listing.

9.3.1. Serum Chemistry, Hematology, and Coagulation

Quantitative serum chemistry, hematology, and coagulation results by treatment group using descriptive statistics at baseline and at each post-baseline visit. The change and percentage change from baseline will also be summarized.

9.3.2. Inflammatory Biomarkers

Inflammatory biomarker ([Appendix 10](#)) results, change from baseline, and percentage change from baseline will be summarized in the same manner described in [Section 9.3.1](#).

9.3.3. Shifts in CTCAE Grade

Quantitative laboratory tests will be assigned grades based on CTCAE Version 4.03, where applicable. Shifts in CTCAE grade of laboratory tests will be presented from baseline to worst post-baseline value, last post-baseline value, best post-baseline value, and at each post-baseline visit. Summaries will present the number and percentage of subjects with shifts in laboratory grade by treatment group. Denominators for percentages will be the number of subjects with non-missing data at the specific assessment and baseline.

These summaries of shifts in CTCAE grade will be repeated for general baseline subgroups as described in [Section 6](#).

In addition, for each laboratory test the number and percent of subjects with a lab value with CTCAE grade ≥ 3 and the number and percent of subjects with a CTCAE shift of ≥ 2 grades will be presented.

Where applicable, if the quantitative criteria for grading are equivalent for two grades, only differentiated by clinical interventions, the clinical intervention will be ignored and the highest CTCAE grade will be used.

For urine protein, values of TRACE or NEGATIVE will be considered normal.

9.3.4. Shifts in Normal Range

In addition, for laboratory tests that cannot be graded via CTCAE, shift tables (i.e., low-normal-high at baseline versus low-normal-high at post-baseline visit in a 3-by-3 contingency table) from baseline to worst post-baseline value, last post-baseline value, best post-baseline value, and at each post-baseline visit will be presented for by treatment group. Denominators for percentages will be the number of subjects with non-missing data at the specific assessment and baseline.

9.3.5. Pregnancy Testing and Urinalysis Dipstick

All pregnancy test results and urinalysis dipstick results will not be summarized but will be provided in a by-subject data listing.

9.4. Weight and BMI

Weight (kg), BMI (kg/m^2), and mBMI ($\text{kg}/\text{m}^2 \text{ g/L}$), defined as a subject's weight (kg) \times subjects squared height (meters) \div serum albumin (g/L), will be summarized by treatment group using descriptive statistics at baseline and at each post-baseline visit. In addition, change and percent change from baseline will be presented.

9.5. Vital Signs

Vital sign parameters including temperature (C), systolic and diastolic pressure (mmHg), pulse (beats/min) and respiratory rate (breaths/min) will be presented in a data listing. Method of collection will be provided in the listing, however summaries will be generated without regard to the method of collection. Pulse pressure, the difference between diastolic and systolic blood pressure, will be calculated. Mean arterial pressure will be calculated as the pulse pressure, divided by 3, plus the diastolic blood pressure.

Summaries of vital sign parameter results, change from baseline, and percentage change from baseline will be summarized by treatment group using descriptive statistics at baseline and at each post-baseline visit. In addition, change and percent change from baseline will be presented from pre-dose to post-dose at each infusion visit.

9.6. Electrocardiograms

ECGs measurements will be made in triplicate, 5 to 10 minutes apart and assessed by a central reader. For summary purposes the mean of the three measurements will be used. ECG parameters including time between 2 consecutive R waves [RR], PR interval, QRS duration, QT (uncorrected) interval, QT interval corrected by the Bazett's formula [QTcB], and QT interval corrected by the Fridericia's formula [QTcF] will be summarized by treatment group. Descriptive statistics will be presented for observed values and changes from baseline at each post-baseline time point.

A categorical summary of the following abnormal maximum mean triplicate QTcF values will be presented by treatment group: >450 msec, >480 msec, and >500 msec. Change from baseline summaries will also be presented for measurements that represent a change from baseline of >30 msec and >60 msec. Three separate listings for those subjects with any QTcF >450 msec or a QTcF change from baseline >30 msec, any QTcF >480 msec or a QTcF change from baseline >30 msec, and any QTcF >500 msec or a QTcF change from baseline >60 msec will be presented. The observation(s) meeting criteria for inclusion will be flagged in the listing.

QTcF will be assigned grades based on CTCAE Version 4.03, without regard to the clinical assessment necessary for Grade 4. Shifts in QTcF CTCAE grade will be presented from baseline to worst post-baseline value, last post-baseline value, and at each post-baseline visit. Summaries will present the number and percentage of subjects with shifts in grade by treatment group. Denominators for percentages will be the number of subjects with non-missing data at the specific assessment and baseline.

Overall interpretation results for ECGs and the investigator interpretation results are collected as normal, abnormal not clinically significant, and abnormal clinically significant. Subjects whose interpretation shifts from normal to abnormal clinically significant or not clinically significant will be listed separately including description of the abnormality and any associated comments.

All ECG results will be presented in by-subject data listings.

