4 SELECTION, DISCONTINUATION, AND WITHDRAWAL OF SUBJECTS

4.1 Inclusion Criteria

Subjects must meet *all* of the following criteria:

1. Age \geq 18 years
2. Confirmed diagnosis of systemic AL amyloidosis by the following:
 - Histochemical diagnosis of amyloidosis determined by polarizing light microscopy of green birefringent material in Congo red-stained tissue specimens **OR** characteristic electron microscopy appearance

AND

- Confirmatory electron microscopy **OR** immunohistochemistry **OR** mass spectrometry of AL amyloidosis
3. If the subject meets *any* of the following criteria, confirm diagnosis of AL amyloidosis by mass spectrometry or immunoelectron microscopy of amyloid material in tissue biopsy:
 - Is black or African American
 - Is over 75 years of age (at time of diagnosis) with concurrent monoclonal gammopathy
 - Has a history of familial amyloidosis and has concurrent monoclonal gammopathy

OR

- If the subject meets any of the above 3 conditions and has echocardiographic evidence of amyloidosis, biopsy-proven amyloidosis with a monoclonal gammopathy and no tissue is available for mass spectrometry or immunoelectron microscopy, the subject must have gene sequencing consistent with transthyretin (TTR) wild type (e.g., no TTR mutation present) **AND** must score 0 in technetium-99m-3,3-diphosphono-1,2 propanodicarboxylic acid (^{99m}Tc -DPD; Rapezzi et al, 2011), hydroxymethylenediphosphonate (^{99m}Tc -HMDP; Galat et al, 2015), or pyrophosphate (^{99m}Tc -PYP; Bokhari et al, 2013) scintigraphy
4. Cardiac involvement as defined by BOTH of the following:
 - Past documented or presently noted clinical signs and symptoms supportive of a diagnosis of heart failure in the setting of a confirmed diagnosis of AL amyloidosis in the absence of an alternative explanation for heart failure
 - Either an endomyocardial biopsy demonstrating AL amyloidosis **OR** an echocardiogram demonstrating a mean left ventricular wall thickness at diastole >12 mm in the absence of other causes (e.g., severe hypertension, aortic stenosis), which would adequately explain the degree of wall thickening

5. NT-proBNP ≥ 650 pg/mL and ≤ 5000 pg/mL (i.e., ≥ 76.7 pmol/L and ≤ 590 pmol/L)
6. Received at least one prior systemic chemotherapeutic regimen, which may include stem cell transplant, for AL amyloidosis

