4.2 Exclusion Criteria

Subjects must *not meet any* of the following criteria:

1. Diagnosis of non-AL amyloidosis
2. Meets the International Myeloma Working Group (IMWG) definition of Multiple Myeloma ([Appendix 3](#))
3. Symptomatic orthostatic hypotension that in the medical judgment of the Investigator would interfere with subject's ability to safely receive treatment or complete study assessments
4. Myocardial infarction, uncontrolled angina, uncontrolled ventricular arrhythmias, or electrocardiographic evidence of acute ischemia, within 6 months prior to the Month 1-Day 1 Visit
5. Severe valvular stenosis (e.g. aortic or mitral stenosis with a valve area <1.0 cm²) or severe congenital heart disease
6. ECG evidence of acute ischemia or active conduction system abnormalities *with the exception* of any of the following:
 - First degree atrioventricular (AV) block
 - Second degree AV block Type 1 (Mobitz Type 1/Wenckebach type)
 - Right or left bundle branch block
 - Atrial fibrillation with a controlled ventricular rate (uncontrolled [i.e., >110 bpm] ventricular rate is not allowed [determined by an average of three beats in Lead II or 3 representative beats if Lead II is not representative of the overall ECG])
7. Has not recovered (i.e., equivalent to a CTCAE ≥Grade 2) from the clinically significant toxic effects of prior anticancer therapy. *Exception:* subjects with prior bortezomib treatment may have CTCAE Grade 2 neuropathy.
8. Received any of the following within the specified time frame prior to the Month 1-Day 1 Visit:
 - Oral or intravenous antibiotics, antifungals, or antivirals within 1 week, *with the exception* of prophylactic oral agents. Note: In the event that a subject requires the chronic use of antivirals, Medical Monitor permission is required for entry into the study.
 - Hematopoietic growth factors, transfusions of blood or blood products within 1 week
 - Chemotherapy, radiotherapy, or other plasma cell directed therapy within 6 months
 - ASCT within 12 months

- Major surgery within 4 weeks
 - Planned major surgery or organ transplant during the study
 - Any other investigational agent within 4 weeks
 - Prior treatment with NEOD001, 11-1F4, anti-SAP antibody (*exception*: allowed as part of established diagnostic procedures such as SAP scintigraphy), or other investigational treatment directed at amyloid
 - Doxycycline within 6 weeks
9. Active malignancy *with the exception* of any of the following:

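### The separate ECG-worsening listing in SAP 9.6 omits shifts from abnormal not clinically significant to abnormal clinically significant, and no other planned output flags or tabulates that shift by arm

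*SAP*

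**What the plan says.** SAP 9.6 sets out what is collected: "Overall interpretation results for ECGs and the investigator interpretation results are collected as normal, abnormal not clinically significant, and abnormal clinically significant". The rule for the separate listing follows: "Subjects whose interpretation shifts from normal to abnormal clinically significant or not clinically significant will be listed separately". The listing is to carry a description of the abnormality and any comments.

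The same section plans other ECG output:

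- Full listings: "All ECG results will be presented in by-subject data listings".
- By-arm summaries of RR, PR, QRS, QT, QTcB and QTcF: "Descriptive statistics will be presented for observed values and changes from baseline at each post-baseline time point".
- Categorical QTcF thresholds, and one shift table: "Shifts in QTcF CTCAE grade will be presented from baseline to worst post-baseline value, last post-baseline value, and at each post-baseline visit".

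Twelve-lead ECG is a named safety assessment (Protocol 3.2.5, SAP 2.3.5). On the population, inclusion criterion 4 in Protocol 4.1 reads "Cardiac involvement as defined by BOTH of the following". The first limb is "Past documented or presently noted clinical signs and symptoms supportive of a diagnosis of heart failure", and the second is a positive endomyocardial biopsy or a thickened ventricular wall on echocardiogram. Exclusion criterion 6 in Protocol 4.2 bars acute ischemia and active conduction abnormalities on ECG, with four exceptions: first-degree AV block, Mobitz type 1 second-degree block, bundle branch block on either side, and atrial fibrillation with a controlled rate.

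**The concern.** A listing meant to draw attention to ECG deterioration should catch a move into the worst category from either lower level. This one catches it only from normal. It lists a subject who goes from normal to NCS, a change that by its label is not clinically significant, and passes over a subject who goes from NCS to CS.

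The restriction matters more here than in a trial of people with healthy hearts. Every subject has cardiac amyloid involvement, and the entry criteria expressly allow several findings that would ordinarily make a baseline ECG abnormal. A reviewer who takes the separate listing as the record of interpretation worsening would be looking at a subset chosen by baseline status, with nothing beside it to show the rest.

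**Working it through.** **1. Transitions.** Three ordered levels give 3 × 2 / 2 = 3 possible worsening moves.

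| Move | In the separate listing? |
|---|---|
| normal to NCS | yes |
| normal to CS | yes |
| NCS to CS | no |

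Coverage is 2 of 3.

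**2. Does any other planned output show the third move?**

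- Full by-subject ECG listings (SAP 9.6): the records are there, but nothing marks a worsening and nothing is counted by arm.
- Interval summaries (SAP 9.6): by arm, with change from baseline, whatever the baseline interpretation. They describe PR, QRS, RR and QT as continuous values, not the interpretation category.
- QTcF thresholds and CTCAE grade shifts (SAP 9.6): QTcF only.
- Adverse events (Protocol 7.1, SAP 9.2): by arm, but dependent on the investigator reporting the event.

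None of these isolates NCS to CS or tabulates interpretation worsening by arm.

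**3. The SAP's practice for comparable variables.** SAP 9.3.4 gives laboratory tests without a CTCAE grade a 3-by-3 shift table by arm, from baseline to worst, last and best values and to each visit. SAP 9.3.3 does the like for graded laboratory tests, and SAP 8.10.8.2 for ECOG, NYHA class and renal stage. ECG interpretation is also an ordered three-level variable, and it has no shift table.

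**4. Two ambiguities in the rule.** The sentence does not say whether a shift is counted from baseline or between any two visits. Nor does it say whether the overall or the investigator interpretation drives it. A direct NCS to CS move is left out on either reading of the first ambiguity.

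**5. How many subjects could be affected.** Inputs: planned N of up to 130 (Protocol 3.3), and the share *a* with an abnormal baseline interpretation. The documents do not give *a*, so it is an assumption. If shifts are counted from baseline, the number outside the listing is 130 × *a*:

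| *a* | 130 × *a* |
|---|---|
| 25% | 32.5, about 32 |
| 50% | 65 |
| 75% | 97.5, about 98 |
| 90% | 117 |

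These are people who could not enter the listing, not people expected to worsen. Anyone already at CS at baseline has no higher level to move to, so the number whom a wider rule could add is at most this count.

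**The case against.** The strongest reply is that little is lost. Every interpretation is listed by subject. PR, QRS and RR, which bear on AV block and bundle branch block, are summarized by arm without regard to baseline interpretation. Protocol 7.1 counts among adverse events both worsening of a preexisting abnormality and new clinically significant findings in physiological testing. SAP 9.2 includes worsening severity in its definition of a treatment-emergent event and tabulates such events by arm. First-degree block that becomes a clinically significant block should therefore be counted whatever the baseline ECG. Cardiac hospitalizations, including those for arrhythmia, are compared by arm under SAP 8.10.8.1. Safety output is descriptive unless otherwise specified.

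Most of this stands, and it rules out three stronger conclusions that a reader might draw:

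- **That this worsening is missing from the analysis.** It is missing from one listing and from any tabulation of interpretation, not from all output.
- **That NCS to CS is the main ECG harm in this trial.** The documents give no expected rate for any transition. Criterion 4 concerns heart-failure signs with biopsy or wall thickness, not ECG reading. Criterion 6 permits four findings and excludes other active conduction abnormalities; being permitted does not show that they are common.
- **That most subjects could never appear in the listing.** The baseline share is unknown. If shifts are counted between visits, a subject abnormal at baseline who later reads normal and then abnormal could still qualify.

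The reply does not remove the gap. A full listing that flags nothing does not do the work of the separate one; if it did, the separate one would not be needed. Means of PR or QRS can hide a few subjects who deteriorate. The adverse-event route depends on reporting: Protocol 6.6.1.3 expressly requires clinically significant physical-examination changes to be recorded as adverse events, while the ECG section, 6.6.1.5, has no such instruction.

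**Conclusion.** The point holds as a minor gap in safety reporting. The separate listing covers two of three worsening transitions, and no planned output flags the third or tabulates interpretation worsening by arm. This follows from the wording of SAP 9.6 alone and needs no assumption about how many subjects start abnormal. The range of about 32 to 117 of 130 is an illustration. It rests on an assumed baseline share of 25% to 90% and on counting shifts from baseline. There is no effect on alpha, power, or the primary or other efficacy analyses, and no data are lost.

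**What to change.** In SAP 9.6, replace the listing rule with one that takes every subject whose ECG interpretation worsens by at least one level from baseline: normal to NCS, normal to CS, or NCS to CS. State whether the overall reading, the investigator reading or both are used. Add a 3-by-3 shift table by treatment group, from baseline to worst post-baseline and to each visit, modelled on SAP 9.3.4.

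The cost is one rewritten sentence and one added table. The interpretations are already collected, so no new assessments are needed.

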9.7. Physical Examination

Analysis of disease-related symptoms collected on the Physical Examination eCRF are detailed in Section [8.10.8.4](#).

Other physical examination findings based on body systems entered on the eCRF will be included in a data listing only.

9.8. Immunogenicity Analyses

Immunogenicity of NEOD001 will be assessed by anti-NEOD001 antibody levels. Any sample found to be confirmed positive for anti-NEOD001 antibodies will be further evaluated by a neutralizing antibody assay. Serum anti-NEOD001 antibody levels will be listed and, if sufficient data exist, summarized by treatment group. Serum anti-NEOD001 antibody levels may be correlated with serum NEOD001 concentrations and select safety endpoints, if sufficient data exist.

10. CHANGES TO PROTOCOL PLANNED ANALYSES

Per Protocol A3, Section 8.3.4: “All exploratory quantitative endpoints, except the 6MWT.... will be analyzed in the same manner described for the SF-36v2...”. The exploratory analyses of LVEF are performed per Section 8.10.1.2 of this SAP.

Appendix 4 of the protocol, footnotes a and b, state “In addition to the progression criteria listed above, the investigators will use their best clinical judgment in circumstances that do not meet the specifically referenced criteria above in assessing the progression. A repeated assessment at an interval that is determined by the investigator is required to confirm the progression.” and “Subjects with progressively worsening renal function cannot be scored for NT-proBNP progression.” Repeat assessments were only done using local laboratories and therefore not included in the central laboratory data for inclusion in analyses. In addition, per the SAP renal progression is not considered for the primary endpoint analyses and is only included as a sensitivity analysis.

Renal endpoints other than renal response will be repeated for the ITT population.

The Safety Population was updated to use treatment received for all subjects instead of randomized treatment.

The following endpoints were removed:

- Time to eGFR ≤ 15 mL/min/1.73 m² (Chronic Kidney Stage 5)
- Time to doubling of creatinine
- Time to peripheral neuropathy organ progression
- Time to peripheral neuropathy organ response
- Time to hepatic organ progression
- Time to hepatic organ response
- Hematologic response at each visit
- Hematologic best response through 3, 6, 9, and 12 months of treatment
- Mayo Clinic Stage including any subgroup analyses
- Peripheral neuropathy best response through 3, 6, 9, and 12 months of treatment

